9.8. Inpatient assessment (post-randomisation and before discharge home)

During the inpatient stay, the following data will be collected from all of the participants and recorded into the electronic study database:

- 1. **Bloods:** including full blood count (FBC), C reactive protein (CRP), liver and renal profile are advisable to be carried out every other day in the first week and weekly or twice per week if staying more than one week as part of usual NHS care (not requested specifically for the study) and based on treating physician discretion.
- 2. **Imaging:** Thoracic Ultrasound on day 3 (+/- 1 day) and 5 (+/- 1 day) or at the time of discharge, and chest x ray on day 3 (+/- 1 day) or as needed based on the discretion of the treating physician.
- 3. Cumulative volume of pleural fluid drainage (over the entire time of the drain being in situ)
- 9. **Antibiotics:** treatment received including types of antibiotics, and duration of intravenous antibiotics if available
- 10. Any chest tube displacement or blockage
- 11. Details of treatments given e.g. whether all intrapleural treatment was completed, any missed or adjustment doses, date and type of surgery, reason surgical intervention was not undertaken, time from randomisation until surgery
- 12. Time from chest drain insertion to IET and/or surgery
- 13. Details of any subsequent pleural interventions while inpatient
- 14. Requirement for surgery due to treatment failure on objective criteria

9.9. Subsequent Visits (Outpatient follow up)

Follow Up (applicable to both arms)

- 1. On discharge, all patients should be followed up in pleural clinic at day 14 and 28 +/- 3 days post discharge with assessments of blood parameters (CRP, liver and renal profile, FBC), chest x-ray and thoracic ultrasound as per standard NHS care.
- 2. A telemedicine review via phone will occur at 90 +_ 3 days post-discharge to collect longer-term outcomes.

3. *The total length of antibiotic treatment given* will be determined by local physicians and clinical response, but it is suggested to be at least 3 weeks total treatment (as per national standards).

Follow Up (Intervention arm only)

In the intervention arm, a clinical review will be arranged in 3 days +/- 2 days after discharge for low RAPID score group participants where bloods (CRP, full blood count, renal and liver profile), thoracic ultrasound and chest x ray will be conducted and the treatment failure criteria will be applied at the time of follow up, should any of these criteria full filled, the participant will be admitted to hospital and treated as intermediate to high score group.

Below is the summary of assessments in each outpatient visit which will be recorded into electronic CRF (REDCap).

Assessment	Day 3 +/-2 days follow up (Low RAPID score group only), post discharge	14 days +_ 3 days follow up	28 days +_ 3 days follow up	90 days +_ follow up (phone call)
Clinical assessment (review symptoms and clinical examination)	Yes	Yes	Yes	NA
Thoracic ultrasound	Yes (part of the research)	Yes (standard care)	Yes (standard care)	NA
Blood (FBC, U and Es, liver function and CRP) – standard NHS care	Yes	Yes	Yes	NA
Chest x ray	Yes	Yes	Yes	Yes (remote review)
Readmissions to hospital	Yes	Yes	Yes	Yes (remote review)
Requirement for further chest drain insertion	Yes	Yes	Yes	Yes (remote review)
Requirement for surgery	Yes	Yes	Yes	Yes (remote review)
Mortality rate	Yes	Yes	Yes	Yes (remote review)
Health related quality of life using EQ-5D-5L	NA	Yes	Yes	Yes (remote review)
Assessment of functional ability (SF36)	Na	Yes	Yes	Yes (remote review)
VAS score pain and breathlessness	NA	Yes	NA	Yes (remote review)

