Secondary	1. Length of hospital stay strategies.	1. Review completeness of data regarding the time of the participants staying in hospital over 3 months from randomisation until discharge.	1. From time of admission to hospital discharge
	2. Mortality rate over 3 months (all cause)	2. Proportion of participants who died (all cause) over 3 months post randomisation.	2. Until the end of the study
	3. Need for IET	3. Proportion of participants who required IET post randomisation	3. From time of admission until discharge
	4. Need for surgery	4. Proportion of participants who required surgery post randomisation	4. From time of admission until discharge

5. Medical	5. Proportion of participants who	5. From time of
treatment failure	did not respond to medical treatment (pleural fluid drainage + IET) and required surgery post randomisation.	admission until discharge
6. Need for repeat intervention and admission	6. Number of participants who need further pleural procedure e.g chest drain insertion or therapeutic thoracocentesis and proportion of the participant who required re admission to hospital.	6. Until the end of the study
7. Duration of antibiotics	7. Review completeness of data regarding the use of antibiotics from start date of antibiotics to date that has been stopped.	7. From day of starting antibiotics up to 6 weeks post discharge
8. Time to complete recovery and return to normal function	8. SF36 measurements	8. At 4 and 12 weeks post randomisation
9. Health related quality of life	9. EQ5D 5I questionnaire	9. At baseline, 2, 4 and 12 weeks post randomisation
10. Mean change and standard deviation in breathlessness and pain	10. Serial measurement of 100mm VAS score for breathlessness and pain	10. Post randomisation and until discharge from hospital
11. To assess feasibility of delivering the intervention arm (RAPID driven arm)	11. Record time of failure of medical treatment to surgery (VATS, thoracotomy) or time from ICD insertion to IET	11. End of the study
12. Healthcare utilisation	12. Number of pleural procedures and days in hospital post randomisation	12. During hospital stay

	13. To assess the pattern of computed tomography of the chest (CT chest) in pleural infection	13. Computed tomography of the chest to assess for consolidation	13. During hospital stay
	e.g., consolidation 14. Radiological changes following treatment	14. Chest x- Ray to assess for pleural thickening	14. At 12 weeks post randomisation

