9. PROTOCOL PROCEDURES

The following table illustrates scheduled study related procedures and data collection

Procedure		Consent	Innetions	Follo	ow up visits		
	Screening	Baseline/ Randomisation	Inpatient Assessme	3 days¹	14 days	28 days	90 days
			nt(s)	+/- 2 days	+/- 3 days	+/- 3 days	+/- 3 days
Eligibility assessment	X	Х					
Informed consent	X ²	X ²					

Demographics R	х	Х					
Medical history ^R	Х	Х					
Clinical assessment R	Х	X	Х	X	Х	Х	Х
Concomitant medication ^R	X3	X ³					
Imaging routine – chest x ray R		Х			Х	Х	Х
Imaging routine – Thoracic Ultrasound ^R		Х	X (on days 3±1 and 5±1 post randomisatio n)	X	X	X	
Imaging routine – CT chest ^R	X ⁴	X ⁴	X ⁴				
Chest drain insertion or therapeutic aspiration in situ or planned	х	X					
Intrapleural enzyme therapy ^R			х				
Surgery ^R			Х				
Routine clinical bloods	Х	Х	х	Х	х	Х	
Routine pleural fluid ^R	Х						
Randomisation		X					
RAPID score		X ⁵					
Research pleural fluid collection and storage		Xe	X ₆				
Research blood collection and storage		X ⁶	X _e				
Breathlessness and/or pain (VAS) score		X ⁷			X ⁷	X ⁷	X ⁷

QOL: EQ-5D-5L	X ₈			X8	X8	X8
---------------	----------------	--	--	----	----	----

Assessment of functional ability (SF36)			X 9	X 9	X ⁹
Health utilization		Х			
Semi- structured interviews				X ¹⁰	

^R Indicates procedures or data collection that is part of routine care for all patients. The results of these are required to be collected and documented as part of the RAPTOR - f study, hence are included in this table.

¹ This will be applied to the low RAPID score group, please see the protocol for the details

² Informed consent will be taken within the first 24 hours after discussing the study and offering the participant information sheet.

³ If the participant had any antibiotics prior to admission to the hospital or if they are on anticoagulation or antiplatelet.

⁴ CT scan will be conducted as part of the usual care for all participants with pleural infection during the inpatient stay

⁵ The RAPID score will be calculated for the intervention group ONLY following randomisation.

⁶ The research samples (paired pleural fluid and blood) will be collected on day 1 (randomisation day) 0,3 and 5 post- randomisation (with the first week). This is optional, please see the protocol for the details of the process.

⁷ These assessments will take place in person at baseline, 14 days +/- 3, 28 days +/-3 days and remotely in 90 days +/- 3 days, please see protocol.

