9.10. Health-related quality of life questionnaires

All patients will be asked to fill in a health-related quality of life (EQ-5D) questionnaire, time to return to normal function (SF36) and a VAS scoresheet for chest pain and breathlessness.

EQ-5D-5L

The EQ-5D is a 5-domain questionnaire which gives an overall assessment of an individual's quality of life at a particular time point. There are five questions, and it is envisaged this should take between 1-2 minutes to complete. These assessments will take place in person at baseline, 14 days +/- 3, 28 days +/-3 days and remotely in 90 days +/- 3 days.

VAS score

RAPTOR – f study uses a VAS score instrument to record patients' reported chest pain and shortness of breath. The patient will be asked to mark on a line scale their assessment of their symptoms at that time. This should take around 30 - 45 seconds per scale. These will be collected at baseline, day 28 + -3 days in person and day 90 + -3 days (remotely)

SF36

This survey assesses eight health concepts: physical functioning, bodily pain, role limitations due to physical health problems, role limitations due to personal or emotional problems, general mental health, social functioning, energy/fatigue, and general health perceptions. It takes 6 to 8 minutes to fill out, this assessment will take place at day 28 + _ 3 days and day 90+_ 3 days.

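### EQ-5D, SF-36 and VAS follow-up is dated from discharge in Section 9.9 but EQ-5D and SF-36 from randomisation in the synopsis, and the VAS day list differs in four places

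*Protocol*

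**What the plan says.** **Anchor.** Section 9.9 sets the clinic contacts with "On discharge, all patients should be followed up in pleural clinic at day 14 and 28 +/- 3 days post discharge" and adds "A telemedicine review via phone will occur at 90 +_ 3 days post-discharge". Its table assigns EQ-5D, SF-36 and VAS to these contacts. The synopsis (Section 3) times EQ-5D "At baseline, 2, 4 and 12 weeks post randomisation" and SF-36 "At 4 and 12 weeks post randomisation". The schedule in Section 9 and the text of Section 9.10 give day numbers without naming an anchor.

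**VAS days.** Four places give four answers:
- Synopsis, outcome 10: "10. Post randomisation and until discharge from hospital". The schedule has no inpatient VAS after baseline.
- Schedule row and footnote 7: "These assessments will take place in person at baseline, 14 days +/- 3, 28 days +/-3 days and remotely in 90 days +/- 3 days".
- Section 9.9 table: days 14 and 90, with day 28 marked as not applicable.
- Section 9.10: "These will be collected at baseline, day 28 + -3 days in person and day 90 + -3 days (remotely", with no day 14.

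**Other instruments.** SF-36 at day 14 is marked in the schedule row and in the Section 9.9 table, but is absent from footnote 9, Section 9.10 and the synopsis. For EQ-5D, only footnote 8 omits day 14. Footnotes 7 and 8 carry the Section 9.10 wording for EQ-5D and VAS respectively but are attached to the opposite instruments, so they appear to have been swapped.

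**Use.** Section 13.1.1 plans adjusted between-group differences with 95% confidence intervals and says the outcomes will inform the definitive trial. The progression table in Section 13.1.2 has a data-completion row that names the VAS as its example: green from 98%, amber 75% to 97%, red below 75%. Section 13 says no separate analysis plan will be used, so the protocol itself has to settle the timing.

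**The concern.** Discharge happens after randomisation, and the RAPID pathway is designed to bring it forward. If scores are dated from discharge, the arm that goes home sooner is also measured sooner after randomisation. A difference in recovery is then mixed with a difference in elapsed time, in an illness where patients improve over weeks. The second planned comparison, low against moderate-to-high RAPID, is exposed too, because early discharge is part of the low-risk pathway only.

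The VAS conflict has a separate consequence. A completeness percentage needs a list of expected forms. With several lists in force, the same conduct gives different percentages, and these percentages feed a stop/go decision.

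**Working it through.** **1. The protocol's own figures.** Section 13.2 assumes a mean stay of 14 days (SD 10) and an 8-day reduction in the 50% of the RAPID arm at low risk: 0.5 × 8 = 4 days overall. At 5% two-sided significance and 90% power, n per arm = 2 × (1.960 + 1.282)² × 10² / 4² = 131.4, rounded up to 132, or 264 in total. This reproduces the stated number, and nothing below alters it. The assumed mean stays are 14 days in standard care and 14 − 4 = 10 days in the RAPID arm.

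**2. Time since randomisation under the Section 9.9 anchor.** Take randomisation as close to admission (an assumption). Day since randomisation = length of stay + nominal day after discharge.

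| Contact after discharge | Standard care (stay 14) | RAPID arm (stay 10) | Gap |
|---|---|---|---|
| 14 | 28 | 24 | 4 |
| 28 | 42 | 38 | 4 |
| 90 | 104 | 100 | 4 |

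The 4-day gap exceeds the 3-day half-width of the window. For low-RAPID patients the protocol's assumed reduction of 8 days gives a gap of 8 days. If randomisation comes later than admission, the absolute days fall, but the gap stays the same as long as the delay is equal on average in the two arms.

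**3. Week 12 and day 90.** 12 × 7 = 84. The window 90 ± 3 runs from 87 to 93. Even with a common anchor, the two timepoints do not meet.

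**4. Can the randomisation timing be met as scheduled?** Section 5 gives a median stay of 12 to 15 days, with 25% of patients in hospital for more than a month. Many will still be inpatients at week 2 and some at week 4, yet the schedule's inpatient column contains none of the three questionnaires.

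**5. VAS denominator.** Assume 30 participants, every form completed as the chosen section asks, and baseline counted (Section 9.4 collects it). Expected forms are 30 × 4 = 120 for the schedule, 30 × 3 = 90 for Section 9.9 plus baseline, and 30 × 3 = 90 for Section 9.10. The synopsis wording gives no countable number.

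| Forms collected under | Scored on schedule | Scored on 9.9 + baseline | Scored on 9.10 |
|---|---|---|---|
| Schedule (0, 14, 28, 90) | 120/120 = 100% | 90/90 = 100% | 90/90 = 100% |
| 9.9 + baseline (0, 14, 90) | 90/120 = 75% | 90/90 = 100% | 60/90 = 66.7% |
| 9.10 (0, 28, 90) | 90/120 = 75% | 60/90 = 66.7% | 90/90 = 100% |

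On the VAS component, full compliance with one section can therefore be green, at the bottom edge of amber, or red. If baseline is not counted, 75% becomes 60/90 = 66.7% and 66.7% becomes 30/60 = 50%.

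**The case against.** Several stronger readings are tempting, and the documents do not support them.

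- *A 12-day gap between arms.* A low-RAPID patient home at 48 hours is seen on about day 2 + 14 = 16, against day 28 for an average standard-care patient. That sets one risk group against the average of all risk groups. The arm-level figure is 4 days.
- *Three-month mortality is compromised.* Deaths can be counted from their dates, and a call 90 days after discharge generally comes no earlier than 90 days after randomisation. The synopsis also follows mortality to the end of the study.
- *Outcome 10 has no data.* Baseline and follow-up VAS are collected, and Section 6 sets no time limit. Only the synopsis timing lacks matching inpatient measurements.
- *Section 6 also conflicts.* Its table has no timepoint column, so the EQ-5D and SF-36 anchor conflict is with the synopsis only.
- *The whole completion row is capped at 75%.* The VAS is an example in that row, so the ceiling applies to the VAS component alone.

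It is also fair to say that all sites use one REDCap database, so a mismatch between collection and scoring needs the form build and the analysis to follow different sections. This is a 30-patient feasibility study, the instruments are secondary, and no tests are planned. The footnote swap may explain part of the VAS and EQ-5D inconsistency.

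These points limit the harm but do not remove it. Swapping the footnotes back leaves the VAS row mark at day 14, the Section 9.9 table and the synopsis unreconciled, and does not touch the anchor. Estimates with confidence intervals are still planned, and the progression criterion still has no fixed VAS denominator.

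**Conclusion.** The contradiction is in the current text and should be corrected. With the discharge anchor, questionnaires would be completed about 4 days apart between arms in time since randomisation, against a window of ±3 days, and further apart for low-RAPID patients. This rests on the protocol's assumed stays of 14 and 10 days; the absolute days also rest on randomisation near admission. With the randomisation anchor the nominal gap is zero.

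For the VAS, compliance in full with one section can score 100%, 75% or 67%, assuming 30 participants with baseline counted. This bears on the VAS part of the completion criterion, not on the row as a whole. The harm is to the descriptive between-arm estimates, to the questionnaire data meant to inform the definitive trial, and to a stop/go measure. The 264-patient calculation is unaffected.

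**What to change.** - Date EQ-5D, SF-36 and VAS from randomisation, completed on the ward or by telephone where needed. Leave the clinic visits as they are.
- State one timepoint list per instrument, identically in the synopsis, the schedule with its footnotes, Section 9.9 and Section 9.10. This includes settling SF-36 at day 14 and correcting footnotes 7 and 8.
- Align week 12 with day 90, so that one timepoint and one window apply.
- Either schedule inpatient VAS measurements or remove the limit at discharge from outcome 10.
- Use the agreed list as the denominator for data completion. For 30 participants, a four-point VAS list gives 120 forms, with at most 2 missing for green (118/120 = 98.3%). A three-point list gives 90 forms, with at most 1 missing (89/90 = 98.9%).

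The cost is a protocol edit and a change to the date rules in the electronic forms. The real downside is that some questionnaires will no longer coincide with a clinic visit. With shorter stays in one arm, the place and mode of completion may differ between arms, so both should be recorded with each form.

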	15. To assess if levels of pleural fluid and blood biomarkers (suPAR, PAI-1, IL 1+2, and NET) will predict treatment failure	15. The proportion of participants with an elevated level of pleural fluid and blood biomarkers in serial samples taken on day 1 (randomisation day), 3 and 5(post - randomisation) who did not respond to medical treatment.	15. During hospital stay and while the chest drain in situ (optional).
Intervention(s)	In the intervention arm, following randomisation, a baseline RAPID score will		

Intervention(s)

In the intervention arm, following randomisation, a baseline RAPID score will be calculated (see Table 1). According to the score, participants will be allocated into two groups, as outlined below. The subsequent treatment will be determined by the calculated RAPID score.

Low RAPID score group:

- Admission for drainage Therapeutic aspirate or short-term chest tube insertion for 24 hours and subsequent tube removal if there are no features of sepsis syndrome or significant residual collections, see predefined treatment failure criteria below.
- Early discharge home within 24 to 48 hours of admission if they meet the proposed discharge criteria (see page 26) and they will be provided with a 24/7 contact number for the clinical study fellow if they have any concerns.
- Review in clinic within 3days +/- 2 days, if any features of medical treatment failure are present, they will be admitted to hospital and treated as a medium-high risk score group.

Medium – high RAPID score group:

- Admission for drainage Chest tube insertion
- Intrapleural instillation of recombinant human deoxyribonuclease (DNAse) 5mg BD (diluted in 30mls sterile water) and Recombinant human tissue plasminogen activator (tPA, Alteplase) 5-10mg BD (diluted in 30mls sterile water) intrapleural immediately after chest drain insertion if deemed safe and no contraindication e.g. no active bleeding or bleeding disorder.

	 Surgical referral at time of chest tube insertion for consideration of Video Assisted Thoracoscopic Surgery (VATS) or open surgery. 	
Comparator	Standard care and intergroup comparison in the RAPID driven arm.	

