9.6. Blinding and code-breaking

There is no blinding in this study, hence no un-blinding procedures or code-breaking are required.

9.7. Description of study intervention(s), comparators and study procedures (post-randomisation and inpatient period)

Intervention arm

In the intervention arm, treatment will be determined according to the calculated baseline RAPID score.

Patients with a higher RAPID score (and thus higher predicted mortality and morbidity (7,12)) will be triaged to more aggressive treatment early in the disease, and those with lower predicted mortality and morbidity will be treated less aggressively.

A. Low risk (RAPID score 0 to 2):

Patients will be treated as follows:

- 1. Pleural drainage: therapeutic pleural aspiration (drain to dryness) using a Rocket kit will be suggested as the initial treatment. If the patient has already had a chest tube inserted prior to randomisation (as randomisation can occur for 24 hours after drain insertion), then patients will be admitted for drainage for a proposed maximum of 24 to 48 hours, with the removal of the drain as soon as possible, provided there is no residual collection of pleural fluid on the chest-xray (CXR) or thoracic ultrasound or CT scan before drain removal. No specific size of drain is specified, and local practice should be followed.
- 2. **Broad spectrum antibiotics**: see below for the expected standard of care in both intervention groups concerning antibiotics, which are as per NHS standard care for pleural infection. Use of early oral antibiotics to promote discharge is recommended in this group.
- 3. **Review at 3 days +_ 2 days post-discharge** with bloods including full blood count, CRP (Creactive protein), liver and renal profile, ultrasound scan and chest x ray.
- 4. **Patient contact:** All patients will receive a 24-hour contact number (to the study fellow) who can be contacted should there be any concern or deterioration when at home which will prompt urgent review by the pleural service locally.

If at any point a patient is considered to have *failed treatment* on the basis of predefined criteria (see below), they will then be treated as per the intermediate/high-risk group below and will be admitted to hospital.

B. Intermediate + high-risk (RAPID score 3 to 7)

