The intermediate and high-risk groups have been combined for the treatment algorithm; there are similar numbers of patients in the combined intermediate and high risk group and the low-risk group (7). Patients in this category will be treated as follows:

- 1. **Pleural drainage:** all patients will be admitted to hospital for chest drain insertion and remain in hospital for as long as is clinically required while the tube is in situ. No specific size of drain is specified, and local practice should be followed.
- 2. Broad spectrum antibiotics: see below; IV antibiotics can be given while the patient is admitted.
- 3. Adjunctive therapy:
 - a. Intrapleural enzyme therapy (tPA / DNase) should be started as soon as possible after drain insertion and randomisation, assuming there are no contraindications. if there is no risk of bleeding.

b. In parallel, referral to local thoracic surgical services made at the time of randomisation, and the need for surgery clinically revisited at 48 hours post-randomisation.

c. In patients where there are contraindications to intrapleural enzyme therapy, immediate surgical intervention in suitable patients should be considered.

Standard care arm:

In the standard care group, the RAPID score *will not be routinely calculated*, and all patients will undergo treatment as per current national guidelines (BTS 2023) (1). This is summarized as follows:

- 1. **Pleural drainage:** all patients will be admitted to the hospital for chest drain insertion and subsequent drainage
- 2. Broad spectrum antibiotics: see below
- 3. **Clinical review** of progression will occur 48 to 72 hours after randomisation and initial above treatment. If there is evidence of poor clinical response (on the objective criteria listed below), the patient will be escalated to either intrapleural therapy or surgical intervention according to patient suitability and clinician choice / usual practice.

Treatment applicable to both arms

A number of treatments should be considered best practice and routine management in patients with pleural infection and will be applied to both groups (intervention and standard care). These treatments follow the NHS standard of care for pleural infection and are as follows:

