- 1. **Broad spectrum antibiotics** to cover both aerobic and anaerobic organisms, and according to infection setting (community or hospital acquired infection), to be focused once culture results are available if positive as per local treatment guidelines or policies.
- 2. Intravenous antibiotics should be given during initial admission (if admitted)
- 3. **Switch to oral antibiotics** should occur once there has been a good clinical response with biochemical and radiological improvement, OR if the patient is intended for outpatient treatment (e.g. low RAPID group).
- 4. **Prophylactic low molecular weight heparin** should be administered as per local protocols if the patient is admitted.
- 5. **Analgesics** including NSAIDS or paracetamol in conjunction with opioids if needed will be provided for pain relief from pleural procedures and chest drains.
- 6. **Nutritional support** (supplements, dietician referral, nasogastric feeding) should be considered as clinically appropriate.
- 7. **Chest drain management**; for all patients who have chest drain during treatment, flushes and thoracic suction should be used according to local practice.
- 8. **Clinical review** should be conducted every day by the treating physician.

Treatment failure Criteria

During treatment and follow-up, the following objective criteria will be used to record if the patient is failing treatment and requires further intense treatment including re-admission, intrapleural enzyme therapy or surgical intervention. These criteria apply to any patient at any point from randomization to four weeks follow-up, and regardless of which treatment arm they have been randomised to (and applied in general around 72 hours post randomisation for standard care and medium-high RAPID score in the intervention arm and at day 3 +_ 2 days post-discharge for low RAPID score group or at any other time if the treating physician feels they failed medical therapy). This measure is in place to ensure patient safety and objectivity of decision-making.

The treatment failure criteria are **BOTH** of the following:

- 1. The presence of a **significant residual pleural collection** on radiology (chest radiograph, ultrasound and/or CT) as judged by the local investigator AND
- 2. **At least one** of the following criteria (more than one may apply):
 - a. Clinical evidence of **ongoing sepsis** with persistent fever, tachycardia or hypotension.

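### Low-RAPID patients are readmitted at the day-3 review on any one failure sign (Section 9.9, Synopsis), although Section 9.7 defines treatment failure as two components together

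*Protocol*

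**What the plan says.** Section 9.7 (Treatment failure Criteria) sets a conjunctive rule: "The treatment failure criteria are BOTH of the following". The first component is a significant residual pleural collection on imaging. The second is at least one of ongoing sepsis, a CRP that has not fallen by 50% from 48 hours after treatment, or an inadequate white-cell response. The rule covers "any patient at any point from randomization to four weeks follow-up, and regardless of which treatment arm they have been randomised to", lists readmission among the responses to failure, and names the visit at issue: "at day 3 +_ 2 days post-discharge for low RAPID score group".

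Elsewhere in Section 9.7, the low-risk pathway moves a patient up if they have failed "on the basis of predefined criteria (see below), they will then be treated as per the intermediate/high-risk group below". The standard care arm uses the same list: "If there is evidence of poor clinical response (on the objective criteria listed below), the patient will be escalated".

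Section 9.9 (Follow Up, Intervention arm only) says that the treatment failure criteria are applied at the low-RAPID review, and then: "should any of these criteria full filled, the participant will be admitted to hospital and treated as intermediate to high score group". The Synopsis, under the low RAPID score group, says: "if any features of medical treatment failure are present, they will be admitted to hospital and treated as a medium-high risk score group".

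**The concern.** The same patients at the same visit are under two rules. Section 9.7 needs a residual collection and another sign; Section 9.9 and the Synopsis, read as written, need only one item from the list. Both looser texts make admission mandatory, so physician discretion does not explain the difference.

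The consequence for the patient is substantial. The intermediate/high-risk pathway in Section 9.7 means a chest drain, enzyme therapy as soon as possible unless contraindicated, and surgical referral. Under the looser rule a patient with no significant collection can be sent down that route.

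The consequence for the data has a direction. Readmission is part of secondary outcome 6, and Section 13.1.1 plans two comparisons of clinical outcomes: standard care against RAPID-driven care, and low against moderate-to-high RAPID. Only the low-RAPID group would face the lower threshold, so its readmission proportion would rise because of the rule rather than the patients' course. Adherence to allocated treatment is also a progression criterion (Section 13.1.2), and one action at this visit could comply with one section and deviate from another.

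**Working it through.** **1. The two rules side by side.** There are four signs: collection (C), sepsis (S), CRP non-response (R) and white-cell non-response (W). Each is present or absent, giving 2^4 = 16 patterns.

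| Rule | Triggers when | Patterns that trigger |
|---|---|---|
| Section 9.7 | C and at least one of S, R, W | 1 × (2^3 − 1) = 7 |
| Section 9.9, Synopsis | at least one of C, S, R, W | 16 − 1 = 15 |

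All 7 patterns under Section 9.7 are among the 15, so the looser rule never removes a readmission. The rules disagree on 15 − 7 = 8 patterns: a collection alone (1), and some combination of S, R and W without a collection (7). These are counts of patterns, not of patients.

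**2. Can a correctly discharged patient fall in the gap?** The Synopsis plans "Early discharge home within 24 to 48 hours of admission if they meet the proposed discharge criteria". With the review at 3 ± 2 days after discharge, the time from admission to review is:

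- earliest: 1 + (3 − 2) = 2 days
- latest: 2 + (3 + 2) = 7 days

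The CRP sign counts from 48 hours after treatment. If treatment starts at admission (an assumption), it is already in force at the earliest permitted review. The discharge criteria in Section 9.7 ask only for a significant reduction in inflammatory markers as judged locally, with no 50% figure. Illustration with assumed values: CRP falls from 300 to 180, a fall of (300 − 180)/300 = 40%. With no significant collection this patient has not failed under Section 9.7, but is readmitted and escalated under Section 9.9.

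**3. Effect per patient on the readmission proportion.** The Synopsis gives 15 patients per arm. Section 13.2 expects half of the RAPID arm to be low risk: 0.5 × 15 = 7.5, so 7 or 8.

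| Patients readmitted only under the looser rule | Low-RAPID group | RAPID arm |
|---|---|---|
| 1 | 1/8 = 12.5% to 1/7 = 14.3% | 1/15 = 6.7% |
| 2 | 2/8 = 25.0% to 2/7 = 28.6% | 2/15 = 13.3% |

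**4. How often the rules might disagree.** The protocol gives no frequencies. Suppose that a collection, and at least one of the other signs, are each present with probability p, independently. Then Section 9.7 triggers with probability p² and the looser rule with 1 − (1 − p)².

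| p (assumed) | Section 9.7 | Looser rule |
|---|---|---|
| 10% | 1% | 19% |
| 20% | 4% | 36% |
| 30% | 9% | 51% |

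If the two components tend to occur together, the gap narrows; if they always coincide, it is zero. The table shows how far apart the rules can lie and is not a forecast.

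**The case against.** The strongest reply is that Section 9.9 does not set a second rule. The same sentence first says that the treatment failure criteria will be applied, a term defined in Section 9.7, which emphasises that both components are required and names this visit. The low-risk pathway in Section 9.7 also refers to predefined criteria, and the Synopsis points to them in the same block. On this view the looser wording is careless English, and few clinicians would send a patient with nothing to drain for a drain and enzyme therapy. This makes Section 9.7 the likely intention. It does not settle the matter, because the mandatory wording appears twice, once in the section that staff would use at this visit.

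A second reply is that the arms already differ. Standard care patients have no day-3 visit after discharge (their first is at day 14), and several signs are judged locally. Readmission would therefore not be perfectly comparable under either rule. That stands, but Section 9.7 applies one definition, including for readmission, to both arms up to four weeks. The looser wording departs from it in one subgroup only.

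It is also true that the per-patient percentages would hold for any event in groups this small, that the discharge criteria make some discordant patterns uncommon, and that readmission is part of one secondary outcome in a study reported without hypothesis tests. A lower threshold for readmitting patients sent home early may even be prudent. These points limit the importance of the problem. They do not make the two rules agree.

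**Conclusion.** The contradiction is real and lies in the current text. Section 9.7 requires two components; Section 9.9 and the Synopsis act on one, for the same patients at the same visit.

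If the looser wording is followed literally, the direction is certain: more low-RAPID readmissions, never fewer. The size is known only per patient, at 12.5 to 14.3 points in the low-RAPID group and 6.7 points in the RAPID arm, given 15 patients in the arm and half of them low risk. The number of patients affected cannot be derived from the protocol and could be zero if sites read Section 9.9 in the light of Section 9.7.

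This should be fixed: it determines treatment at a safety visit, and the readmission and adherence figures are meant to inform a definitive trial.

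**What to change.** In Section 9.9 and in the low RAPID score group text of the Synopsis, replace the looser condition with: if the treatment failure criteria in Section 9.7 (both 1 and 2) are met. State that the physician may still readmit at any time on clinical grounds, and record such readmissions separately from treatment failure.

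If a more cautious trigger is wanted for patients sent home early, write it as a separate readmission rule with its own treatment, and do not call it treatment failure.

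The cost is a wording amendment in two places and, unless the eCRF (not shown) already captures it, one field for the reason for readmission: Section 9.7 failure or physician discretion. No extra procedures are needed, because bloods, ultrasound, chest x-ray and readmissions are already recorded at this review.
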